7.2 Primary objectives

- To determine the that the future RCT is feasible, we will conduct a feasibility study to test the ability to consent parents and children and follow up the children in 10 schools, rating child emotional and behavioural problems using the Me and My Feelings questionnaire (M&MF, Deighton et al 2013), as well as wellbeing (using The Children's Outcome Rating Scale, CORS, Duncan, Miller & Sparks, 2003)

7.3 Secondary objectives

- Teacher measures: To validate a teacher rating of whole class behaviour
- Estimate parameters to determine sample size for a full trial
- Validate classroom-based outcome measure
- Standardise teacher adherence rating
- Validate child quiz

8. Trial Design

8.1 Design

The design will be a parallel group feasibility cluster RCT with random allocation of schools to one of two arms, in a 1:1 ratio.

The usual school curriculum will be delivered without interference in both conditions, with assessments at baseline (0-weeks), 8-weeks and 16-weeks (post intervention, primary endpoint) and a proposed primary outcome of emotional and behavioural problems for vulnerable children at 16-weeks. Waitlist control participants will be offered the intervention later in the term or the following school year. The intervention will be delivered to whole classes; each school will be two or three form entry, and thus comprise two or three classes. Each class will comprise around thirty children

PROTOCOL IDENTIFICATION Amendment number: Original V1 Issue date: 251021 Authors: [name] Amendment I 010322: Figures for feasibility amended to proportions; proportion of children giving baseline data added (as logical follow-on from parental consent/child assent rates).

Schools will be randomised to classes receiving CUES-Ed, in addition to the usual school curriculum, either now (CUES-Ed) or later (waitlist control, WL). The usual school curriculum is nationally set, with limited scope for variation by school. We will record what is delivered in the usual curriculum, but will not interfere with usual delivery. In particular, as CUES-Ed will not comprise additional hours of teaching, we will record any difference arising in the routine curriculum delivered in intervention and control schools.

Trained research workers will complete assessments with children and teachers at baseline (T0), 8-weeks (T1) and 16-weeks (T2, post therapy), see Figure 1.

We will not be able to blind participants or teachers to treatment group. The RAs completing outcome assessments will also not be blinded to treatment allocation, as there are usually indicators in the classroom when children have received the intervention, and the children talk about the intervention. Once collected, data will be processed by a RA fully blind to allocation. These RAs will be shielded from discussions where the possibility of unblinding might arise. Information on allocation will be restricted to the trial co-ordinator and maintained in a separate database from outcome measures. Breaks of blind procedure will be monitored, and an alternative data processor identified for the subsequent assessments. We will ask RAs to guess allocation group for each school as a test of the success of our efforts to maintain blindness. We will report any instances of unblinding in subsequent publications.

8.2 Trial Flowchart

	Engagement with school	Baseline 0-weeks	Pre-intervention	0-16 weeks	8-weeks	16-weeks
Headteacher consent	X					
Parent letter, opt-out/consent option	X					
Teacher liaison/consent	X					
Child assent		X				
Randomisation			X			
Intervention				X		
Assessment measures						
Primary outcome (proposed): Child-rated emotional and behavioural problems (Me and My Feelings)		X				X
Secondary outcome: Child-rated emotional and behavioural problems (Me and My Feelings)					X	
Secondary outcome: Child-rated wellbeing (Child outcome rating scale)		X			X	X
Secondary outcome: Teacher-rated classroom behaviour		X			X	X
Secondary outcome: Child-rated quiz		X			X	X

9-15: METHODS: PARTICIPANTS, INTERVENTIONS, OUTCOMES

9. Study setting

We will approach primary schools in London and the home counties, run by Local Education Authorities, who are known to the CUES-Ed service. We will aim to recruit differing schools, to estimate variability in outcome between schools for the larger trial which will recruit nationwide.

Once Local Education Authorities have agreed for us to contact schools in their area, we will contact headteachers. For the feasibility pilot, we are contacting schools who know of the CUES-Ed service, as they will be well-placed to feedback on the impact of trial procedures. We expect to be approaching local authorities *at least six weeks*

before the anticipated randomisation date for a school and headteachers and teachers at least a month before.

Headteachers will be asked for their agreement to participate on behalf of their school. Headteachers will consult with teachers of Year 4 children before agreeing to participate, to ensure willingness to deliver the intervention. Once headteachers have consented on behalf of the school, teachers will be asked formally for their consent separately.

Once headteachers and teachers have consented, the school will be considered to be participating in the study.

At least two weeks before randomisation, participating schools will send information sheets and consent forms to parents by their usual method for sending school-based permissions (paper letter and/or email).

- Information sheets will inform parents of the school's decision to deliver the intervention as part of a randomised controlled study, and to complete evaluation measures. Parents will be offered the option to remove their child from the CUES-Ed teaching and assessments if they wish, but will not be asked to consent to this.
- Parents will be asked for consent to use their child's self-report measures for a research purpose.
- Consents will be returned to the school by the school's usual method of return of other school-based permissions. In addition, the research team will be present at the school gates during drop-off and pick-up times to take consent forms directly.

At the same time as parent information sheets are sent out, children will be told about the study by their teacher, using a video from the study team to ensure key information is covered.

Baseline assessments will commence *two weeks after* parental consents are sent out, to ensure parents have time to opt out of CUES-Ed teaching and assessments should they wish to.

- Children will be asked for assent for data use, and also given the opportunity to withdraw from the CUES-Ed intervention and assessment at the first baseline assessment.
- If any child is considered by the class teacher to be expressing a wish not to participate, in either the intervention or assessment, this will be dealt with at the teacher's discretion, as the teacher is responsible for the children's wellbeing and safety during the school day. As part of the school consent, withdrawn children will be found an alternative classroom activity. The teacher information sheet will make clear to teachers that participation in the study should not change their usual treatment of children, outside delivery of the intervention. We expect requests to remove children to be rare: in service delivery of CUES-Ed to 6,000 children has generated only two parental withdrawals, and no child withdrawals. Unless withdrawn, children will otherwise complete

the intervention and assessments. In this way, children will not feel stigmatised by being excluded from the class-based intervention and evaluation by not consenting to the use of data for research. Data for children without parental consent or not assenting will be kept separately and confidentially by the school and securely destroyed without sight by the research team.

- Teacher ratings are based on a whole class and the collection and use of these for a research purpose will be covered by the headteacher consent. The research team will liaise with the school administration to access returned consent forms. School consents will include agreement for the school office to follow-up non-returned consents and to ask permission for the research team to be in touch to support completion.

10. Eligibility

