6.1.2 CUES-Ed intervention

CUES-Ed is an innovative prevention and early intervention programme rooted in evidence-based Cognitive Behaviour Therapy (CBT) and designed by Clinical Psychologists as a result of direct feedback gathered over many years from children we have worked with in Child and Adolescent Mental Health

CUES-Ed is designed for delivery to whole classes of primary-aged children (7-10 years) to ensure they learn useful ways of looking after themselves and their mental health. They are taught by clinical psychologists or CBT therapists to understand when things are not going well and develop life-long skills to help manage any difficulties now and those that might emerge later in adolescence or adulthood. While all children are expected to gain some benefit, vulnerable children within the class are the key target group for change.

Learning about mental health needs to start from an early age for it to be most effective – and we have found a way of engaging children in a creative and interactive way – with exciting, visually strong and recognisable branding and characters that promote mental health in a positive way.

Across eight whole-class sessions, children learn cognitive strategies and simple but effective behavioural techniques through fun hands-on activities that make abstract concepts more concrete and memorable.

We promote flexible and adaptive responses to difficulties, including self-regulation (the ability to monitor and manage thoughts, behaviours and emotions; especially important when things are difficult or when strong emotions take over) and support-seeking - recognising when extra help is needed. These approaches encourage children to learn the skills that can help build their resilience from an early age. The CUES-Ed workbook for children, parent newsletters, weekly home-tasks and digital development reinforce the key concepts at school and home and promote long-term retention of learning.

Feedback on CUES-Ed from teachers:

"This program has been meaningful and with a clear purpose. The impact on the children cannot be underestimated – this program has not been an 'add on', but has really started to change the attitudes of the children."

"All the children have been able to access the course. They have learned strategies and vocabulary to help them. They have become more confident in recognising and talking about their feelings and are applying their strategies in class, the playground and at home."

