6.1.4 Feasibility of the intervention: safety, acceptability and potential helpfulness

CUES-Ed has been delivered in person to over 6000 primary school children in 78 schools to date, primarily across South London – see Appendix 2 for a full list of the schools we have worked with.

Service evaluation (Redfern et al 2019) shows high ratings of acceptability by children and teachers and improvements on whole class mental health knowledge and well-being. Children’s written feedback suggested benefits in emotional literacy, understanding how to look after their mental health, normalising emotional responses to confusing/difficult experiences, and emotion-regulation strategies.

Feedback on CUES-Ed from children:

“I think my mind is a whole lot calmer and I’m much more aware of my thoughts, my feelings and my behaviours. You have inspired me to tell my family and friends about what we have been doing...”

“I never thought there were so many ways to calm down!”

“CUES-Ed has made me understand more about my feelings and also how to handle my emotions when times are tough. I am very grateful for the CUES-Ed team because they have helped me very much.”

Importantly, children identified as more vulnerable consistently show significant improvement following the CUES-Ed programme. Vulnerability was defined as those scoring within a clinical range on self-report measures of wellbeing/distress. The Children’s Outcome Rating Scale (CORS, Duncan, Miller & Sparks, 2003) measures wellbeing/distress across four items, each rated 0 (worst) to 10 (best); clinical cut-off <32. Me and My Feelings (Deighton et al., 2013) comprises 16 items, each rated 0 (best) to 2 (worst), measuring emotional (M&MF-E) and behavioural (M&MF-B) difficulties (M&MF-E, ten items; borderline/clinical cut-off >9; M&MF-B, six items; borderline/clinical cut-off >5).

See table below:

Measure	n	% of cohort	Pre-Mean (SD)	Post-Mean (SD)	p
Wellbeing / distress	227	45%	22.98 (6.68)	26.56 (8.64)	<0.01
Emotional difficulties	144	28%	11.9 (2.45)	9.99 (3.33)	<0.01
Behavioural difficulties	100	20%	7.43 (1.46)	6.04 (2.44)	<0.01

Key: SD=standard deviation

In-service clinic data for over 3,000 children receiving CUES-Ed showed whole class benefits of children being better able to look after themselves, improved emotional literacy and an increased repertoire of coping strategies. Improved general well-being, emotional well-being and behaviour was found for vulnerable children.

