10.1 Inclusion Criteria

The school and child inclusion criteria are shown as follows:

School (cluster) inclusion criteria:

- Run by the Local Education Authority/borough, providing mainstream education.
- In London or the home counties
- With an intake at Year 4 (children aged 8-9 years) and Year 5 (children aged 9-10 years)

Student inclusion criteria:

- All children in Year 4 (aged 8-9 years)

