10.2 Exclusion Criteria

School (Cluster) exclusion criteria:

- Private or specialist schools.

Student exclusion criteria:

- None

11. Trial Intervention

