12.1 Primary outcome measures

For the feasibility outcomes the parameters are based upon the following progression criteria:

Criteria	Green (Go)	Amber (Proceed with changes)	Red (Not feasible to proceed)
Randomise schools	10	8	<8
Consent/Baseline data for children from parents	360/600=60%	240/600=40%	<240/600
Child assent	360/600=60%	240/600=40%	<240/600
Children providing baseline data	360/600=60%	240/600=40%	<240/600
Followed up	%80	70%	<70%
Adherence of teachers	%80	70%	<70%
Fidelity of intervention*	%80	70%	<70%

* Fidelity is determined by whether CUES-Ed schools get CUES-Ed and waitlist control schools do not get CUES-Ed between 0-16 weeks

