13.4 Study flow diagram

Figure 1: Design

14. Sample size

We estimate from two classes within 10 schools there will be approximately 600 children and we anticipate that 60% of parents of the children will consent (n=360). We anticipate the key challenge to the success of running the future confirmatory RCT will be to understand the follow up rate. By consenting and collecting baseline data from 360 children we will be able to estimate the follow up rate (assumed to be 80%) with $\pm 4.1\%$.

15: Recruitment

15.1 Schools:

For the feasibility pilot study, we will recruit schools known to the CUES-Ed service, by liaising directly with local authorities and headteachers. Each school will be approached for headteacher consent. Teachers will be approached by their head to discuss participation. However, as the headteacher is also their manager, they will each have a separate meeting with the research team to ensure they have the opportunity to decline participation should they wish to. Heads will agree, as part of their consent on behalf of the school, to teachers being free to decide to participate or otherwise without this compromising their relationship with their school in any way.

15.2 Parents:

Once headteacher and teacher consent is secured, letters will be sent to all parents in the target year group explaining the study and seeking consent to use outcome measures for a research purpose. Parents will receive one telephone follow-up from the school office – they will be asked if they would be willing for the research team to contact them. Parents agreeing to this contact will also be followed up by the

research team. We will also place research team members in playgrounds during drop-off and pick-up times with additional forms for parents to sign.

15.3 Children:

All children will be invited to attend CUES-Ed sessions and complete outcomes, unless parents, or the children themselves request not to participate. This is because it is important that the parental consent process does not result in children feeling excluded or stigmatised. Children will give assent for the use of the measures for research. This will be given as privately as possible, again to avoid any stigma. We will only use data when both parents and children consent.

METHODS: ASSIGNMENT OF INTERVENTIONS

16. Randomisation

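### Recruitment is limited to schools that know the CUES-Ed service, but Year 4 classes already taught CUES-Ed are neither excluded nor recorded, so either arm could include pre-exposed classes

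*Protocol*

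**What the plan says.** **Sampling frame.** Section 9 states that for the pilot "we are contacting schools who know of the CUES-Ed service", on the ground that such schools are well placed to comment on trial procedures. Section 15.1 repeats the restriction: "we will recruit schools known to the CUES-Ed service".

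**Earlier delivery.** Section 6.1.4 reports that "CUES-Ed has been delivered in person to over 6000 primary school children in 78 schools to date", mainly in South London. The trial recruits in London and the home counties. Section 6.1.2 gives the programme's age range as 7-10 years, and section 6.1.5 adds that a digital version has been piloted.

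**Eligibility.** Section 10.1 admits all Year 4 children, aged 8-9. In section 10.2 the only school exclusion is "Private or specialist schools", and there is no student exclusion.

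**Fidelity.** The footnote to the progression table in 12.1 defines fidelity as "whether CUES-Ed schools get CUES-Ed and waitlist control schools do not get CUES-Ed between 0-16 weeks".

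**Allocation and analysis.** Section 16.1 balances on school deprivation and size. The M&MF model in 20.2 adjusts for baseline score, sex and age. Sections 8.1 and 11.1.1 record the usual curriculum delivered in each arm; they do not ask for a class's CUES-Ed history.

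**The concern.** The programme's age range includes the year before Year 4, and the frame consists of schools in contact with the service. A class entering the trial could therefore have been taught CUES-Ed in Year 3 or earlier in Year 4. Nothing in eligibility, data collection, randomisation or analysis would identify such a class.

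Section 6.2 justifies the waitlist control as a comparison of delivering the programme with not delivering it. A waitlist class taught the programme last year does not represent the second condition. A CUES-Ed class taught last year would be receiving it a second time. The protocol itself expects the effects to last: section 6.1.2 describes skills meant to endure and materials meant to support long-term retention.

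What is at stake is the information passed to the full trial:
- the between-group M&MF summary;
- the M&MF variance and intra-cluster correlation, because unrecorded exposure of whole classes adds variation between schools that a nationwide trial in unexposed schools would not have;
- the quiz validation, because the quiz is meant to measure learning from CUES-Ed and some children might bring that learning to baseline.

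**Working it through.** **1. What this does not touch.** The protocol's only precision figure is ±4.1% for an 80% follow-up rate in 360 children (section 14). It reproduces: 1.96 × √(0.8 × 0.2 / 360) = 0.0413, treating children as independent. Prior CUES-Ed teaching does not enter this calculation, and there is no evident reason for it to move the consent, assent or follow-up proportions much.

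**2. How much earlier delivery there has been.** 6000 / 78 ≈ 77 children per served school. At 30 per class that is 77 / 30 ≈ 2.6 classes. In a two-form school this is 2.6 / 2 = 1.3 year groups over the service's whole history, and in a three-form school 2.6 / 3 ≈ 0.9. So a served school has on average taught about one cohort. The protocol does not say how many approached schools were served, or whether the cohort taught is the present Year 4.

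**3. Effect on the M&MF contrast if control schools are exposed.** Ten schools at 1:1 give five per arm. Let k be the number of exposed control schools, r the share of the full effect that persists, and b the slope of outcome on baseline score. M&MF is measured before randomisation and is a covariate in 20.2, so a benefit already present at baseline is partly removed by adjustment:

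contrast retained = 1 − (k/5) × r × (1 − b)

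The values of k, r and b are assumptions; the protocol gives none. The formula also assumes equal school sizes, no exposed intervention school, and that in-person and digital teaching have the same full effect.

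| r | b | k = 1 | k = 2 |
|---|---|---|---|
| 0.25 | 0 | 0.95 | 0.90 |
| 0.50 | 0 | 0.90 | 0.80 |
| 1.00 | 0 | 0.80 | 0.60 |
| 1.00 | 0.6 | 0.92 | 0.84 |
| 0.25 | 0.6 | 0.98 | 0.96 |

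For example, r = 1, b = 0.6, k = 1 gives 1 − 0.2 × 1 × 0.4 = 0.92.

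**4. Which arm.** Exposed schools may fall in either arm. If two of the ten were exposed, simple 5:5 allocation puts both in control with probability C(8,3)/C(10,5) = 56/252 = 0.22, both in intervention with probability 0.22, and one in each with probability 0.56. The covariate constraint in 16.1 does not target this. An exposed intervention school could raise the contrast, if repeat teaching adds to a retained benefit, or lower it, if little is left to gain from an already improved baseline.

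**5. Can the plan see it?** A waitlist class taught before week 0 and not during weeks 0-16 scores as faithful under 12.1. Section 7.1.1 asks for no contamination but does not define the term or extend it to the time before baseline. The baseline quiz could hint at prior learning, but it is not set up as an exposure check.

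**The case against.** **Exposure is inferred.** Knowing of a service is not the same as having been taught by it, and step 2 shows that even a served school averages only about one cohort. This stands. A reader might infer that the controls are pre-exposed; the documents support only that the plan allows it.

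**The fidelity criterion does its own job.** It asks whether schools followed their allocation over 16 weeks, and a school that did so should score as faithful. This also stands. A reader might conclude that the criterion is defective, but the gap is in eligibility.

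**The loss may be small.** Baseline adjustment absorbs some of a persisting benefit, persistence may be partial, and earlier teaching was by clinicians in person whereas the trial version is digital and teacher-led. This stands and is why a range is given. A reader might square the worst one-school case into a sample-size penalty, 1/0.8² = 1.56. The documents do not support that as a headline: it needs full persistence, exposure in control only and no baseline absorption, and no section says that the pilot's effect estimate will set the full trial's target difference.

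**The choice of familiar schools is deliberate.** It is, and any difference from a nationwide population that comes from familiarity alone is accepted openly. But the stated reason, feedback on trial procedures, does not require the present Year 4 to have been taught. The objection therefore does not answer the gap.

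**Recording would be enough.** Recording makes exposure visible, but an exposed waitlist class still does not represent non-delivery, and five schools per arm leave little room to handle it in the analysis. Recording is the fallback.

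**Conclusion.** The point holds as an eligibility gap. The protocol recruits from schools in contact with a service that teaches this age group, and nowhere excludes, records, balances on or adjusts for earlier CUES-Ed teaching of the enrolled classes. Either arm could be affected.

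The primary feasibility proportions are largely untouched. The exposure falls on the secondary aims: the M&MF summary, the variance and intra-cluster correlation, and the quiz validation. With one of five control schools exposed, about 80% to 95% of the contrast would be retained without baseline absorption (full to 25% persistence), and about 92% with full persistence and a slope of 0.6. These figures rest on assumed persistence, slope and number of exposed schools, and on exposure in the control arm only. How likely any of this is cannot be judged from the protocol. The case for acting is that the gap would go unrecorded and is cheap to close before randomisation.

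**What to change.** In section 10.2, add a school exclusion: the current Year 4 cohort has already received CUES-Ed, in person or in the digital version. Confirm it before randomisation in two ways: with the headteacher at consent, and against the service's list of schools worked with, to which section 6.1.4 refers. As described there, the list is of schools rather than cohorts, so the headteacher's answer is needed as well. Keep the recruitment of schools that know the service.

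Where an affected school cannot be replaced, record prior CUES-Ed delivery by class before randomisation and report it alongside the M&MF and quiz results.

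The cost is one eligibility line, one question at an existing contact and one check against an existing list. The downside is that a few approached schools may become ineligible and need replacing.
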